10.4 Analysis Plan

A full analysis plan will be provided in a separate Statistical Analysis Plan.

Primary safety analyses will be based on all participants who receive at least one dose of vaccine. Safety endpoints will be compared between the different dose groups. The frequency of adverse events will be tabulated by grade and MedDRA System Organ Class and treatment group, and MedDRA Preferred Term and treatment group. Groups will be compared using Fisher's exact test in terms of the proportion ever experiencing an event in each MedDRA System Organ Class.

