8.1.2 EXPECTED ADVERSE EVENTS

The safety and reactogenicity of the IMP is expected to be comparable to the safety observed in previous clinical trials conducted where saRNA have been tested with other vaccine antigens in Phase I clinical trials (COVAC1, COVAC Uganda). See summary table 5 below for systemic and local reactions reported in individuals who received a 5 µg dose of LNP-nCoVsaRNA vaccine.

Up to 100% of participants are expected to experience grade 1-2 systemic reactions including fatigue, myalgia, headaches, chills/shivering and arthralgia. Similarly, close to 100% of participants are expected to experience grade 1-2 local reactions, with pain and tenderness/discomfort likely to be the most common local reactions.

Uncommon reactions include high temperature (≥ 38°C), nausea and vomiting, and erythema and induration at site of injection.

Vasovagal syncope (i.e. fainting), may occur in this population of subjects. It will be attempted to minimise the occurrence of this reaction, by allowing the subjects to lie down during administration of vaccine and blood drawings.

Table 5. Adverse Events in participants the COVAC1 clinical trial who received a 5 μg dose of LNP-nCoV-saRNA

		LNP-nCoVsaRNA dose
		5.0 μg N=24
	Any	
	Normal	0 (0.0%)
	Grade 1	8 (33.3%)
	Grade 2	14 (58.3%)
	Grade 3	2 (8.3%)
	Temperature	
	Normal	21 (87.5%)
	Grade 1	2 (8.3%)
	Grade 2	0 (0.0%)
	Grade 3	1 (4.2%)
	Chills/shivering	
	Normal	10 (41.7%)
	Grade 1	11 (45.8%)
	Grade 2	3 (12.5%)
	Myalgia (flu-like general ı	
	Normal	5 (20.8%)
	Grade 1	13 (54.2%)
	Grade 2	6 (25.0%)
	Grade 3	0 (0.0%)
	Arthralgia	
0	Normal	11 (45.8%)
Systemic	Grade 1	9 (37.5%)
	Grade 2	4 (16.7%)
	Grade 3	0 (0.0%)
	Fatigue	
	Normal	3 (12.5%)
	Grade 1	11 (45.8%)
	Grade 2	10 (41.7%)
	Grade 3	0 (0.0%)
	Sidd 0	0 (0.070)
	Headache Normal	2 (9 20/)
	Grade 1	2 (8.3%) 14 (58.3%)
	Grade 2	8 (33.3%)
	Nausea Normal	19 (79.2%)
	Grade 1	5 (20.8%)
	Grade 2	0 (0.0%)
	Grade 3	0 (0.0%)
		(())
	Vomiting	
	Normal	24 (100.0%)
		24 (100.0%) 0 (0.0%)
	Normal Grade 3	0 (0.0%)
	Normal Grade 3 Any Normal	0 (0.0%)
	Normal Grade 3 Any Normal Grade 1	0 (0.0%) 1 (4.2%) 15 (62.5%)
	Normal Grade 3 Any Normal	0 (0.0%)
	Normal Grade 3 Any Normal Grade 1	0 (0.0%) 1 (4.2%) 15 (62.5%)
	Normal Grade 3 Any Normal Grade 1 Grade 2	0 (0.0%) 1 (4.2%) 15 (62.5%) 8 (33.3%)
	Normal Grade 3 Any Normal Grade 1 Grade 2	0 (0.0%) 1 (4.2%) 15 (62.5%)
	Normal Grade 3 Any Normal Grade 1 Grade 2 Pain Normal	0 (0.0%) 1 (4.2%) 15 (62.5%) 8 (33.3%)

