10.3 Sample Size

10.3.1 SAFETY

It is not the remit of this Phase I trial to recruit a sufficient number of participants to be statistically confident about the differences between groups, and thus no formal hypothesis testing will be carried out for safety. By the end of this trial 8 participants will have been exposed to each vaccine alone or in combinations and this provides confidence around the response/event proportions of 0–100% in Table 7.

Table 7: confidence around the response/event proportions per dose irrespective of schedule

Number of "responders"	Proportion if n=8	95% confidence interval ¹
	11 11-8	
0	0%	0 – 32%
1	12.5%	1 – 47%
2	25%	7 – 59%
3	37.5%	14 – 69%
4	50%	22 – 78%
5	62.5%	31 – 86%
6	75%	41 – 93%
7	87.5%	53 – 99%
8	100%	68 - 100%

¹ Wilson interval (suitable for small sample sizes)

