10.3.2 IMMUNOGENICITY

A total of 40 participants will be included in the randomised evaluation of immunogenicity, 8 participants per group. The primary analysis will compare binding antibody responses to Ebola virus, Lassa virus and Marburg virus glycoproteins at 14 weeks (2 weeks after the booster at 12 weeks). It is difficult to give an estimate of the power of group comparisons using quantitative antibody titre outcomes at this stage as this is dependent on the number of responders, and the large number of experimental parameters in this experimental trial. The main objective of groups 1-5 is to assess whether overall immune responses to individual Ebola, Lassa and Marburg LNP saRNA vaccines given alone are similar to those administered in combination. No formal hypothesis testing will be performed for immunogenicity endpoints; all comparisons will be descriptive. Ideally, binding and neutralisation antibody should be observed in 100% of participants. With a sample size of 8 participants per group, the lower 5% CI for the response rate is 68-100% if there are no non-responders, and 41-93% if there are two non-responders in any group. The number of 'responders' in each assay will be presented for each timepoint and group as a proportion with a 95% confidence interval. A 'responder' will be defined as a participant in whom a response was detected in two weeks after the final vaccination immunogenicity sample. A positive result will be defined relative to a pre-defined cut-off threshold value and assays will be validated using predefined thresholds based on the responses to positive and negative control stimuli. More information on the assay and definition of positive results will be supplied

in the SAP. Titres of antigen specific antibodies will be described by timepoint and group and compared using rank tests, where appropriate.

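### Section 10.4 prescribes Fisher's exact tests on adverse events by System Organ Class, which 10.3.1 rules out; at 8 per group their non-significant p-values must not be read as similar tolerability

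*Protocol*

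**What the plan says.** Section 10.3.1 explains that the trial is not sized to be confident about group differences, "thus no formal hypothesis testing will be carried out for safety". Its numerical basis for safety is Table 7, which gives Wilson intervals for a proportion out of 8.

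Section 10.4 then says that "Safety endpoints will be compared between the different dose groups". It adds a descriptive layer: "The frequency of adverse events will be tabulated by grade and MedDRA System Organ Class and treatment group", and also by Preferred Term. It ends with a named test: "Groups will be compared using Fisher's exact test in terms of the proportion ever experiencing an event in each MedDRA System Organ Class". That sentence carries no condition. It does not say whether the comparison is pairwise or across all five groups, and it gives no significance level.

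On expected rates, section 8.1.2 says: "Up to 100% of participants are expected to experience grade 1-2 systemic reactions". It expects close to all participants to have local reactions. Table 5 supports this with 24 people given 5 μg of the earlier COVID-19 saRNA vaccine.

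**The concern.** An analyst cannot follow both sections: one rules out formal safety testing and the other names a test to be run for every SOC.

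The measure also suits the question poorly. The groups receive between 4 and 13 μg of saRNA in total at each visit. Section 3.1.6.2 reports that reactogenicity with the earlier vaccine was dose dependent and illustrates this with the proportion of Grade 3 reactions. A yes/no count per SOC treats a Grade 1 and a Grade 3 reaction alike. Where nearly everyone reacts, there is almost nothing left for the test to find.

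Safety alone and in combination is the stated aim of the trial. A column of non-significant p-values beside the SOC table invites the reading that the three-vaccine regimen is tolerated as well as one vaccine. Section 10.3.1 itself says that the sample cannot support conclusions of that kind.

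**Working it through.** **Inputs.** There are 8 participants per group in five groups (10.3.2, Table 1). Table 5 gives any systemic reaction 24/24, any local 23/24 (95.8%), headache 22/24 (91.7%), arthralgia 13/24 (54.2%), nausea 5/24 (20.8%), raised temperature 3/24 (12.5%) and vomiting 0/24. Three assumptions are mine: two-sided α = 0.05, solicited reactions entering the SOC tables, and, where no figure is given, illustrative rates such as 10% v 50%.

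**1. The plan's own figures (Table 7).** The Wilson interval is [p + z²/2n ± z√(p(1−p)/n + z²/4n²)] / (1 + z²/n), with n = 8 and z² = 3.84.
- 0/8: upper limit 3.84/11.84 = 32%.
- 8/8: lower limit 8/11.84 = 68%.
- 6/8: 41–93%.

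Seven of the nine rows match the plain formula. The rows for 1/8 and 7/8 match the modified Wilson limit (−ln 0.95/8 = 0.6%, printed as 1%, with its mirror image 99%). Table 7 therefore reproduces.

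**2. Smallest significant split, 8 v 8.**
- 8/8 v 4/8: p = 2 × C(8,4)/C(16,12) = 2 × 70/1820 = 0.077.
- 8/8 v 3/8: p = 2 × C(8,3)/C(16,11) = 2 × 56/4368 = 0.026.

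A 50-point gap from the ceiling is thus not significant; 62.5 points are needed. By symmetry, 0/8 v 4/8 gives 0.077 and 0/8 v 5/8 gives 0.026.

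**3. Pairwise power.** This is the sum of Bin(a; 8, p₁) × Bin(b; 8, p₂) over all splits with p ≤ 0.05. When one group is at 100% it reduces to P(X ≤ 3) with X ~ Bin(8, p).

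| True rates | Power |
|---|---|
| 95.8% v 100% | 0.0006% |
| 91.7% v 100% | 0.02% |
| 90% v 100% | 0.04% |
| 20.8% v 50% | 11% |
| 10% v 50% | 22% |
| 20.8% v 75% | 48% |
| 20.8% v 90% | 78% |

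**4. Five-group version** (Fisher–Freeman–Halton, exact enumeration).
- All five groups at 95.8%: rejection 0.5%.
- Three groups at 91.7%, two at 100%: 2.2%.
- Rates 20.8/20.8/20.8/40/60%: 31%.
- Rates 20.8/20.8/20.8/21/75%: 60%.

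The pattern is the same: next to nothing at the ceiling, low to moderate away from it.

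**5. What grade would add.** In Table 5, systemic Grade 2 or worse was 14 + 2 = 16/24 (67%) and local Grade 2 was 8/24 (33%). These are away from the ceiling, but the sample is no larger: Fisher power is 9% for 67% v 100% and 17% for 33% v 67%.

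**6. What an interval would show.** Newcombe's limits are d − √[(p₁−l₁)² + (u₂−p₂)²] and d + √[(u₁−p₁)² + (p₂−l₂)²], where l and u are the Wilson limits. For 8/8 v 5/8:
- d = 0.375.
- Wilson limits are 0.676–1.000 and 0.306–0.863.
- Lower limit: 0.375 − √(0.324² + 0.238²) = −0.03.
- Upper limit: 0.375 + 0.319 = 0.69.

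The same data give Fisher p = 0.20. The interval shows that a large excess is not excluded; the p-value does not.

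**The case against.** The strongest reply is that the conflict is one of terminology. Section 10.3.1 excludes formal testing, and no safety hypothesis, α or decision rule is stated. Section 10.3.2 follows the same pattern for titres, calling all comparisons descriptive yet allowing rank tests. On that reading the Fisher p-values are nominal, and a complaint about multiplicity has no claimed error rate to act on. This has weight, but the rank tests are qualified by a phrase limiting them to where they are appropriate. The Fisher sentence has no such qualifier, and nothing in 10.4 calls its p-values descriptive. The text still has to be reconciled.

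Four stronger readings are tempting, and the protocol does not support them.
- **That the test cannot separate the regimens at all.** It is applied per SOC. Outside the ceiling SOCs it is underpowered, not incapable: 78% for 20.8% v 90%.
- **That Table 5 puts reactions near 100% in every group.** It is one 5 μg group of a different vaccine, it includes no combination, and it is not arranged by SOC. Arthralgia, nausea, raised temperature and vomiting were well below the ceiling. Carrying the rates over to this trial rests on the expectation in 8.1.2.
- **That this is the only safety comparison and severity is lost.** Section 10.4 also provides for safety endpoints in general to be compared and for events to be tabulated by grade and group. Grade is missing from the named test, not from the reporting.
- **That the groups differ in number of injections.** Section 7.1.2 gives everyone three per visit, with placebo making up the number.

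It is also fair that comparing by grade does not cure n = 8 (steps 5 and 6), and that the choice of contrasts could sit in the SAP. The Fisher sentence, however, is fixed in the protocol.

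**Conclusion.** The point holds in this form: 10.4 contradicts 10.3.1 on safety testing, and the test it names ignores grade. Under the assumptions of two-sided 0.05 and solicited reactions coded into the SOC tables, pairwise power is under 0.1% for 90–96% v 100%. Without the coding assumption, the near-ceiling argument falls away; the contradiction and the low to moderate power at intermediate rates remain. A reader should not take non-significant results over many SOCs as evidence of similar tolerability. The matter should be corrected but does not threaten the trial: the descriptive tables by grade already exist, and the limit on precision is the sample size that 10.3.1 openly accepts.

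**What to change.** In 10.4, delete the Fisher sentence so that the section agrees with 10.3.1. Keep the SOC and Preferred Term tables, with grade, as description. Replace the test with a descriptive comparison by group:
- the number and proportion of participants with maximum grade 2 or worse, and with maximum grade 3 or worse;
- solicited and unsolicited events shown separately, in line with the outcome list in 10.2;
- a Wilson 95% interval for each group, as in Table 7;
- risk differences with Newcombe 95% intervals for Groups 4 and 5 against the single-vaccine groups.

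Add a sentence that these intervals will be wide at 8 per group and that an interval including zero is not evidence of equal tolerability.

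The cost is a wording change in the protocol and matching text in the SAP. Grades are already collected through the diary and adverse event forms, so no new data are needed. What is given up is a set of p-values that 10.3.1 already disclaims.

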11. MONITORING

The trial will be overseen by a Trial Steering Committee (TSC), which will include membership independent of the Trial Management Group (TMG). The reason for this is the need for real-time assessment of the safety data. The TSC will be informed by the Chief Investigator when the first participant receives the first injection of 5 μg, and a report of 7-day reactogenicity will be provided when the first 4 individuals have completed their Week 1 visit (see Section 4.1.1). The TSC will receive weekly progress reports. Weekly reports will continue whilst day 7 data are accumulating; after which point the frequency will be determined by the TSC (in accordance with the TSC Charter). Any adverse reactions that lead to interruption in the schedule for an individual or plan for enrolments described in Section 7.1.4 will be immediately reported to the TSC. The site will be requested to notify the Chief Investigator within 24 hours of any adverse reaction that is a cause for concern as described in Section 8. These reports will be shared with the Trial Steering Committee immediately. If there are 2 out of 8 participants (25% thereafter) who experience similarly severe adverse reactions, vaccinations will be paused in all individuals and the competent authority informed. The TSC will be asked to review the accumulating safety data from all participants and make a recommendation about resuming vaccinations.

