3.5 Rationale for dose selection

The choice of dose is supported by the pivotal toxicology study, showing no observed adverse effect level (NOAEL) for the LNP-MARVsaRNA-01 vaccine is 5 μ g/dose when given alone, and 13 μ g when administered at the same time as LNP-EBOV-saRNA-01 (4 μ g) and LNP-LASSA-saRNA-01 (4 μ g). In addition, data from immunogenicity studies showing that that 5 μ g/dose of LNP-MARVsaRNA-01, LNP-EBOVsaRNA-01 and LNP-LASSAsaRNA-01 were well tolerated and induced robust immune responses. Although there is no toxicology data for vaccination with just Ebola or Lassa saRNA vaccines, the absence of adverse effects when all vaccines are administered on one occasion, provides evidence that these vaccines will be safe when given alone. The LNP-EBOV-saRNA-01 and LNP-LASSAsaRNA-01 will be assessed a 4 μ g/dose to accommodate differences in manufactured concentrations and avoiding volume adjustment in the pharmacy of clinic. From an immunological standpoint the difference between 4 and 5 μ g is unlikely to be significant.

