4.1 Study Design

This is the first-in-human trial of the LNP-MARVsaRNA, LNP-EBOVsaRNA and LNP-LASSAsaRNA vaccine conducted in 18-50 year olds in a single centre with sentinel individuals for each group. Previous studies of our self-amplifying RNA vaccine demonstrated that doses up to 10 μ g were well tolerated [16, 17] and indicated that a 12-week interval between doses was better than a four-week interval with respect to the magnitude of elicited responses [17].

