- 9. At 48 (-/+5) hours post-vaccination the team will call the fourth participant and go through their diaries. If the reactions are Grade 1-2, or transient Grade 3 that resolve within 24 hours, the fifth participant may receive 5 μ g of LNP-MARVsaRNA plus 4 μ g of LNP-EBOVsaRNA plus 4 μ g of LNP-LASSAsaRNA

- 10. At 1 day post immunisation, the fifth participant will attend the trial site to review AEs and donate blood to measure innate immune responses.
- 11. At 48 (–/+5) hours post-vaccination the team will call the fifth participant and go through their diaries. If the reactions are Grade 1-2, or transient Grade 3 that resolve within 24 hours, the dose evaluation cohort of remaining 35 participants may start to be enrolled and randomised into one of the 5 groups to receive their first immunisation.
- 12. Sentinel participants will be evaluated again as above after receiving their second dose. If the reactions are Grade 1-2, or transient Grade 3 that resolve within 24 hours, the cohort of remaining 35 participants may receive their second dose

The steps above describe the fastest plan to enrol into the 5 groups and is justified based on previous experience with this self-amplifying RNA platform. However, if there are persistent Grade 3 reactions observed in any of the sentinels, the team will invite the affected participant to attend the trial site in order to evaluate these and will proceed to vaccinate a second sentinel within the same group. The group will not be changed until at least 1 participant has provided acceptable safety data to at least 48 (–/+5) hours post-vaccination. If 2 or more of the participants at any dose level in this part of the trial have persistent Grade 3 (or worse) reactions, or if 1 or more has a serious adverse reaction, the dose will not be expanded, and the trial stopping rules described below (7.1.5) will be triggered.

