11.1.1 SAFETY AND RIGHTS OF PARTCIPANTS

The pre-clinical data available for LNP-MARVsaRNA, LNP-EBOVsaRNA and LNP-LASSAsaRNA for four species (mice, guinea pigs, rats and pigs) suggest that this product will be similar to licensed RNA vaccines and cause mild-moderate reactions that are transient. However, this is a first-in-human trial and therefore there will be a sentinel cohort with one individual allocated to each group. There will be immediate review of notable and serious adverse events with onward reporting to the TSC, and clear indications for pausing injections in individuals and the trial.

It will be necessary to hold personal contact details in order to collect the data on reactogenicity. The justification for this will be explained in the PIS as well as the storage and destruction of these data after the trial.

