Because this is a first-in-human trial, there will be sentinel participants in each dose group, who will be vaccinated 2 days before any others. The dose evaluation plan is detailed in **Section 4.1.1**.

The rules for pausing and discontinuing vaccinations in individuals and all participants in the trial have been clearly defined.

Participants will be paid for their time, inconvenience and travel expenses: £200 per scheduled visit, paid as a lump sum at the end of participation. This includes any travel expenses they might incur. Volunteers who attend screening but who are not enrolled will not receive payment. If their participation ends early, participants will be paid for the number of visits they've attended.

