13.1 Trial Management Team (TMT)

A Trial Management Team (TMT) will be formed comprising the Chief Investigator, the Scientific Lead, and members of the Clinical Research Facility (CRF) who have a coordinating role. The TMT will be responsible for preparing and reviewing the central data monitoring reports including the safety reports, and for onward reporting to the TMG and TSC. Safety reports will be weekly during vaccination weeks to capture the day 7 reactogenicity, and 2-4 weekly otherwise.

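### The TSC's 7-day report is triggered by four individuals although Section 4.1.1 doses five sentinels, so it need not contain the Group 5 (13 µg) sentinel's 7-day data, and the other 35 may be opened before the TSC has them

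*Protocol*

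**What the plan says.** Protocol Section 11 sets the first defined safety report to the TSC: "a report of 7-day reactogenicity will be provided when the first 4 individuals have completed their Week 1 visit (see Section 4.1.1". The same section promises weekly progress reports and immediate reporting of reactions that interrupt the schedule. Section 13.1 adds: "Safety reports will be weekly during vaccination weeks to capture the day 7 reactogenicity".

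Section 4.1.1, which Section 11 cites, doses one sentinel per group in the order Group 1 to Group 5. Section 11.1.1 agrees: "there will be a sentinel cohort with one individual allocated to each group". Each step depends on a diary call by the team at 48 hours, with a tolerance of 5 hours either way. After the fifth call, step 11 says that "the dose evaluation cohort of remaining 35 participants may start to be enrolled and randomised into one of the 5 groups". Its criterion is the grade of reactions. It names neither a TSC review nor a laboratory result.

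Section 4.1.1 says that these steps "describe the fastest plan to enrol into the 5 groups and is justified based on previous experience with this self-amplifying RNA platform". Section 4.1 gives that experience: "Previous studies of our self-amplifying RNA vaccine demonstrated that doses up to 10" µg were well tolerated. Group 4 receives 9 µg in total and Group 5 receives 13 µg. For the dose itself, Section 3.5 says: "The choice of dose is supported by the pivotal toxicology study".

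**The concern.** The trigger of four does not fit the section it cites. With five sentinels dosed in order, the first four to complete Week 1 are those of Groups 1 to 4. The one whose 7-day data the report does not require is the Group 5 sentinel, who receives the largest total dose and the only one above the stated platform experience. Section 3.1.6.2 says that reactogenicity in the earlier saRNA trial was dose dependent, with the highest proportion of Grade 3 reactions (11%) at 10 µg.

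The timing adds to this. The team may open the cohort on about 2 of the 7 solicited days for the Group 5 sentinel. Section 13.4 forgoes a data monitoring committee and relies on reports to the TSC's independent members, so the content and timing of those reports carry weight. At stake is whether further participants receive 13 µg before the independent members have one person's full week of reactions and first post-dose safety bloods.

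**Working it through.** **Counts.** One sentinel in each of 5 groups gives 5 sentinels. 40 − 5 = 35 remaining, which reproduces the figure in step 11. Total doses: Group 4, 5 + 4 = 9 µg; Group 5, 5 + 4 + 4 = 13 µg. Both match Table 1, and 13/10 = 1.3 times the stated platform experience. The trigger of 4 in Section 11 does not follow from the 5 sentinels.

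**Calendar on the fastest plan.** Inputs are a step of 48 hours (43 to 53; Section 4.1.1) and a Week 1 visit at dose + 7 days, window 0 to +2 (Table 2). Sentinel *i* is dosed after (*i* − 1) steps. Opening is one step after sentinel 5, so 5 steps after the first dose. The range column uses the extremes of both tolerances.

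| Event | At 48-hour steps | Range |
|---|---|---|
| Sentinel doses, Groups 1 to 5 | Days 0, 2, 4, 6, 8 | |
| The 35 may be opened | Day 10 | 9.0 to 11.0 |
| Sentinel 4 Week 1 visit (report trigger) | Day 13 to 15 | 12.4 to 15.6 |
| Sentinel 5 Week 1 visit | Day 15 to 17 | 14.2 to 17.8 |

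From opening to the sentinel 5 Week 1 visit:
- shortest: 168 − 53 = 115 h = 4.8 days
- nominal: 168 − 48 = 120 h = 5.0 days
- longest: 216 − 43 = 173 h = 7.2 days

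The four-person trigger itself falls 2.6 to 5.4 days after opening. Changing four to five without a hold would therefore still leave the report 5 to 7 days late.

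**First post-dose safety bloods.** Table 2 lists no safety bloods on Day 1: that visit's volume is 6 mL, for innate cytokines only. The visit volumes add up as 15 + 82 + 6 + 16 + 16 + 64 + 6 + 16 + 76 + 58 + 16 + 16 + 16 = 403 mL, the total that the protocol states. On Table 2 the first are at Day 7, about Day 15 of the sequence for sentinel 5.

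**Weekly reports.** If the reporting day is arbitrary, a weekly report falls between the sentinel 5 dose and opening with chance 2/7 = 29%, and then holds at most 2 days of that sentinel's data. A weekly report with the Day 7 data follows a Day 15 visit by 0 to 7 days, which is 5 to 12 days after opening.

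**Exposure in the gap.** Assume even accrual over the stated 3 months (91 days) and equal allocation: 35/(91 − 10) = 0.432 per day.
- 5 days: 2.16 participants, 2.16/5 = 0.43 in Group 5
- 7 days: 3.02 participants, 3.02/5 = 0.60 in Group 5
- 12 days: 5.19 participants, 5.19/5 = 1.04 in Group 5

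If enrolment took half that time (assumption), the rate is 35/(45.5 − 10) = 0.986 per day. The Group 5 figures for 5 and 7 days are then 4.93/5 = 0.99 and 6.90/5 = 1.38.

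**The case against.** The 48-hour gate is a deliberate and consistent choice. Section 4.1.1 justifies it by platform experience, and Section 12.2.1 repeats that "there will be sentinel participants in each dose group, who will be vaccinated 2 days before any others". No section promises TSC approval before expansion, so no commitment is broken. The TSC Charter and the safety and monitoring plans, which are not at hand, may add detail. The hold is therefore an improvement to the design, not the repair of a broken rule.

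Other safeguards are real. Under Section 4.1.1 a persistent Grade 3 reaction in a sentinel means a second sentinel in the same group. Two such reactions, or one serious adverse reaction, stop expansion of that dose. Section 9.4 flags Grade 3 diary entries for immediate attention. Section 7.1.5 pauses the trial for two Grade 3 reactions in a group or any serious adverse reaction. These stand, and they keep the stake small.

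Three stronger readings are tempting, and the protocol does not support them:

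- *A reader might infer that the TSC will see nothing of Group 5 before the 35 are opened.* The protocol permits this but does not require it. A weekly report could fall in the window, and a reaction that interrupts the plan is reported at once.
- *A reader might infer that the report excludes the Group 5 sentinel.* Section 11 says when the report is sent, not whose data it may hold. At Day 13 that sentinel's partial diary could be included. Only the 7-day data are not required.
- *A reader might infer that 13 µg is the one dose without human experience.* Section 3.1.6.2 says that none of the three vaccines has been studied clinically. The 10 µg figure comes from another antigen on the same platform. Group 5 stands out only on total saRNA, given as three separate injections, and the triple combination was part of the toxicology study.

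What remains is the mismatch in the trigger, and an expansion step that can come before the data the report should carry.

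**Conclusion.** The point holds in this limited form and is minor. Section 11's trigger does not match the five-sentinel sequence it cites, and the 7-day data it leaves optional belong to the highest total dose. On the fastest plan the 35 may be opened 5 to 7 days before the Group 5 sentinel's Week 1 visit.

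The timing rests on 48-hour steps without delay and on no second sentinel being needed. A second sentinel in Groups 1 to 3 would leave the first four individuals covering only three groups. The exposure, 0.4 to 0.6 Group 5 participants in the gap, rests on even accrual over 3 months. It is 1.0 to 1.4 if enrolment takes half as long.

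**What to change.** 1. In Section 11, trigger the 7-day report on all five sentinel participants, including any replacement sentinel, in place of the count of four.
2. In Section 4.1.1 step 11, make receipt of that report by the TSC a condition for opening the 35. The report should hold the Group 5 sentinel's Day 7 diary and Day 7 safety bloods. The first change alone does not close the gap.

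Holding the whole cohort keeps the five groups concurrently randomised.

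**Cost.** The start moves back by 5 to 7 days plus TSC turnaround. With an assumed 1 to 3 days this is 6 to 10 days, or 6/91 = 6.6% to 10/91 = 11.0% of a 3-month enrolment. It delays all 35, of whom 28 are in groups at or below 9 µg. No visits, samples or participants are added.

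Two separate editorial points can be settled in the same amendment. The platform-experience sentence in Section 4.1.1 could be limited to total doses up to 10 µg, with a reference to Section 3.5 for 13 µg. Section 9.4, which has safety blood taken at every trial visit, should agree with Table 2, which shows none on Day 1.
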